## 4.2. All-cause

All-cause mortality will be summarized in the following table:

	Follow-up time						
	1 month	6 months	12 months	24 months	36 months	48 months	60 months
Alive and in study a							
Dead to date b	before discharge: c						
	after discharge: f						
Censored to date c							
Survival probability d							

aNumber of subjects whose follow-up times are greater than the time point.

bNumber of subjects whose follow-up times are less than or equal to the time point and who are known to be dead.

cNumber of subjects whose follow-up times are less than or equal to the time point and who are not known to be dead.

dThe Kaplan-Meier estimate of the survival curve at the time point, with 95-percent confidence interval. The survival curve gives the probability of surviving past a given time.

eNumber of subjects in this cell whose deaths occurred before discharge (PRTH:DSCHDT).

fNumber of subjects in this cell whose deaths occurred after discharge (PRTH:DSCHDT).

### 4.3. AAA-related

Deaths will be classified as AAA-related based on the following definition:

yes if	death occurs within 30 days of any procedure (initial or secondary) OR
	on the death form, “procedure caused or contributed to death” = yes (DTH:DTCYNP = “YES” and DTH:DTHCTX = “PROCEDURE CAUSED OR CONTRIBUTED TO DEATH”) OR
	on the death form, “device caused or contributed to death” = yes (DTH:DTCYNP = “YES” and DTH:DTHCTX = “DEVICE CAUSED OR CONTRIBUTED TO DEATH”)
no if	death does not occur within 30 days of any procedure (initial or secondary) AND
	on the death form, “procedure caused or contributed to death” = no (DTH:DTCYNP = “NO” and DTH:DTHCTX = “PROCEDURE CAUSED OR CONTRIBUTED TO DEATH”) AND
	on the death form, “device caused or contributed to death” = no (DTH:DTCYNP = “NO” and DTH:DTHCTX = “DEVICE CAUSED OR CONTRIBUTED TO DEATH”)
missing otherwise	

AAA-related mortality will be summarized in the following table:

	Follow-up time						
	1 month	6 months	12 months	24 months	36 months	48 months	60 months
Alive and in study a							
Dead of AAA to date b	before discharge: e						
	after discharge: f						
Censored to date c							
Survival probability d							

aNumber of subjects whose follow-up times are greater than the time point.

bNumber of subjects whose follow-up times are less than or equal to the time point, who are known to be dead, and whose deaths are AAA-related.

cNumber of subjects whose follow-up times are less than or equal to the time point and who are not known to be dead, are dead of a cause unrelated to AAA, or are dead of an unknown cause.

dThe Kaplan-Meier estimate of the survival curve at the time point, with 95-percent confidence interval. The survival curve gives the probability of surviving past a given time.

eNumber of subjects in this cell whose deaths occurred before initial discharge (PRTH:DSCHDT such that PRTH:PROTYP = "INIT IMPLANT").

fNumber of subjects in this cell whose deaths occurred after initial discharge (PRTH:DSCHDT such that PRTH:PROTYP = "INIT IMPLANT").

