#### 7.4. Mortality and secondary interventions

The summary reports will consist of the tables described in sections 4 and 5. The patient-level reports will have one row for each subject and the following columns:

Mortality:

1. study ID (CLNO:PT)
2. Cleveland Clinic ID (CLNO:CLINNO)
3. procedure date (PRTH:PROCDT)
4. discharge date (PRTH:DSCHDAT)
5. date of end of follow-up period, as defined in section 4.1
6. length of follow-up period in months, as defined in section 4.1
7. indicator of whether subject is dead (0 = no, 1 = yes)
8. indicator of whether death is AAA-related, as defined in section 4.3 (0 = no, 1 = yes, NULL = not dead)

Secondary interventions:

1. study ID (CLNO:PT)
2. Cleveland Clinic ID (CLNO:CLINNO)
3. procedure date (PRTH:PROCDT)
4. discharge date (PRTH:DSCHDAT)
5. date of end of follow-up period, as defined in section 5
6. length of follow-up period in months, as defined in section 5
7. indicator of whether subject has had at least one secondary intervention (0 = no, 1 = yes)

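### SAP 4.3 can undercount AAA-related deaths: late deaths of undetermined relatedness are censored with unrelated deaths, and a late rupture death can be classed as not AAA-related

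*SAP*

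**What the plan says.** Section 4.3 sorts deaths into three classes.

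- **Yes**, if any of three conditions holds: "death occurs within 30 days of any procedure (initial or secondary) OR" the death form records "procedure caused or contributed to death" as yes, or it records the same for the device.
- **No**, if all three are negative: "death does not occur within 30 days of any procedure (initial or secondary) AND" both death-form items are answered no.
- Any other death is "missing otherwise".

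Under footnote b of the table, only deaths classed AAA-related are events. Footnote c defines the 'Censored to date' row as subjects not known to be dead together with those who "are dead of a cause unrelated to AAA, or are dead of an unknown cause". Footnote d applies the Kaplan-Meier estimator with a 95% confidence interval.

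Section 4.2 has a parallel all-cause table. Its death row is defined as: "Number of subjects whose follow-up times are less than or equal to the time point and who are known to be dead".

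Section 7.4 lists the patient-level mortality report. Column 7 indicates whether the subject is dead. Column 8 gives AAA-relatedness, coded "0 = no, 1 = yes, NULL = not dead".

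**The concern.** There are two separate routes to an undercount.

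**Unclassified deaths.** Section 4.3 creates a class for deaths whose relatedness cannot be determined, and the table then merges that class with unrelated deaths and with subjects not known to be dead. The estimate treats an unclassified death exactly like an unrelated one, and a reader cannot tell how many there were.

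**Rupture.** The event row is labelled 'Dead of AAA to date', but none of the three 'yes' conditions is death from the aneurysm. They concern timing after a procedure, contribution of the procedure and contribution of the device. A late rupture death with both items answered no passes every part of the 'no' rule.

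If AAA-related deaths are few, one or two deaths handled this way can move the reported figure noticeably.

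**Working it through.** The SAP states no event counts or rates here, so there is no planned figure to reproduce. The check has a logical part, from the SAP text alone, and an illustration on assumed data.

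**1. All combinations under section 4.3.** Within 30 days of a procedure (yes/no) × procedure item (yes/no/blank) × device item (yes/no/blank) gives 2 × 3 × 3 = 18 combinations.

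| Timing | Items | Combinations | Class | In the table |
|---|---|---|---|---|
| Within 30 days | any | 9 | yes | event |
| Later | at least one yes | 5 | yes | event |
| Later | no / no | 1 | no | censored |
| Later | no / blank, blank / no, blank / blank | 3 | missing | censored |

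The three missing combinations cannot be events under footnote b, so they are censored whether or not footnote c's 'unknown cause' was meant as the same class. The SAP does not link the two terms. Read literally, they also conflict: a death of unknown cause within 30 days is an event by the definition but censored by footnote c.

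**2. Rupture.** A rupture death later than 30 days after every procedure, with both items no, falls in the no / no line. Cause of death is not an input to the rule.

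**3. Can the unclassified count be recovered elsewhere?** Subtracting AAA-related deaths (4.3) from all deaths (4.2) gives unrelated plus unclassified deaths combined. In section 7.4, column 7 still marks the subject as dead, but column 8 has no code for a death of unknown relatedness, because NULL is defined as not dead.

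**4. Illustration (all inputs assumed).** 150 subjects. AAA-related deaths at 0.3, 0.7, 8.5, 19.5 and 30.5 months. 20 other deaths evenly spaced from 3 to 35.5 months. 125 subjects followed past 36 months. With n at risk just before each event, S = ∏(1 − 1/n).

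- The numbers at risk at the five AAA-related deaths are 150, 149, 144, 137 and 129.
- Planned rule: S(36) = (149/150)(148/149)(143/144)(136/137)(128/129) = 0.9651, so 1 − S = 3.49%. This does not change with the number of unclassified deaths among the 20.
- One unclassified death counted as an event: if it is the earliest (n = 148), S = 0.9651 × 147/148, giving 4.14%; if the latest (n = 126), S = 0.9651 × 125/126, giving 4.25%.

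| Of the 20, counted as AAA-related | 1 − KM at 36 months (range over which ones) | Cumulative incidence |
|---|---|---|
| 0 (as planned) | 3.49% | 5/150 = 3.33% |
| 1 | 4.14–4.25% | 6/150 = 4.00% |
| 2 | 4.79–5.01% | 7/150 = 4.67% |
| 4 | 6.10–6.47% | 9/150 = 6.00% |

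All-cause mortality is 25/150 = 16.67%. That is an upper bound on the AAA-related figure, but too wide to be useful.

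**The case against.** The strongest counter-arguments are these.

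- **The rupture route is narrow and depends on unseen material.** A rupture followed by a further procedure and death within 30 days is already an event, and so is one that the site attributes to the device. Whether sites would answer no to the device item for a rupture after implantation depends on death-form instructions that the SAP does not give. This stands as a limit on frequency. It does not change what the rule does when both answers are no.
- **Censoring unknown causes is a disclosed choice.** Footnote c states it openly, and counting all such deaths as AAA-related is the opposite extreme. Both points are fair, which is why the planned estimate should stay and the alternative should be shown beside it. Disclosing the rule still does not disclose the number of deaths affected.
- **The row label is only shorthand**, defined through footnote b. This is also fair: the label is not a formal contradiction. The gap lies in the definition behind it.
- **The illustration is one invented cohort.** With the same death times, one unclassified death moves the estimate by about 0.2 points at N = 600 and by 1.6–2.5 points at N = 60. At N = 150 the 95% log-log interval around 3.5% is about 1.5–8.2%, which contains every shift shown. The size is therefore uncertain. But a sampling interval does not measure misclassification.
- **The net bias is not established.** The 30-day condition counts deaths of any cause, and Kaplan-Meier censoring of competing deaths raises the estimate. This stands, and the conclusion is limited accordingly.

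**Conclusion.** The concern holds on the SAP's own text. Followed exactly, section 4.3 censors late deaths of undetermined relatedness together with unrelated deaths, hides their number in the summary tables, and classes a late rupture death with two 'no' answers as not AAA-related. Against complete classification with the same estimator, both rules can only lower the AAA-related death count.

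No claim is made about net bias against true cumulative incidence. In the illustration, the planned 3.5% slightly exceeds the 3.3% incidence if none of the other deaths is truly AAA-related, and falls below the 4.0% incidence if one is.

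The actual size cannot be computed, because the SAP gives neither the number of unclassified deaths nor the number of rupture deaths. On the assumed cohort, two such deaths take the figure from 3.5% to 4.8–5.0%, a relative rise of more than a third. This should be corrected; confidence is medium because frequency is unknown. The coding gap in section 7.4 is minor.

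**What to change.** In section 4.3:

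1. Add death from aneurysm rupture to the 'yes' rule, with the matching condition in the 'no' rule, based on the recorded cause of death. Name the field or source: the only death-form fields the SAP cites are DTHDAT, DTCYNP and DTHCTX.
2. Give deaths of unknown relatedness their own table row, separate from 'Censored to date'. Word footnote c in terms of the missing class, so that it no longer conflicts with the 30-day condition.
3. Keep the planned Kaplan-Meier estimate and place beside it a sensitivity estimate that counts deaths of unknown relatedness as AAA-related.

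In section 7.4, as a minor clarification, give column 8 a separate code for a dead subject whose relatedness is unknown.

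The cost is SAP wording, one table row, one extra estimate and one code. If no cause-of-death field exists, a source for rupture deaths must be found. The reported AAA-related mortality may become slightly less favourable.

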## 5. Secondary interventions

Each patient will have a follow-up time, defined as follows:

- = months from date of initial procedure (PRTH:PROCDT such that PRTH:PROTYP = “INIT IMPLANT”) to date of first secondary intervention (PRTH:PROCDT such that PRTH:PROTYP = “ADD ENDO”), if any secondary interventions
- = months from initial procedure date (PRTH:PROCDT such that PRTH:PROTYP = “INIT IMPLANT”) to death date (DTH:DTHDAT), if no secondary interventions and known to be dead
- = months from initial procedure date (PRTH:PROCDT such that PRTH:PROTYP = “INIT IMPLANT”) to last day of reporting period, if no secondary interventions and not known to be dead

A month will be defined as 30 days.

Secondary interventions will be summarized in the following table:

	Follow-up time						
	1 month	6 months	12 months	24 months	36 months	48 months	60 months
Alive, in study, and free of secondary interventions a							
Has experienced at least one secondary intervention b							
Censored to date c							
Survival probability d							

aNumber of subjects whose follow-up times are greater than the time point.

bNumber of subjects whose follow-up times are less than or equal to the time point and who experienced at least one secondary intervention.

cNumber of subjects whose follow-up times are less than or equal to the time point and and who have not experienced any secondary interventions.

dThe Kaplan-Meier estimate of the survival curve at the time point, with 95-percent confidence interval. The survival curve gives the probability of surviving past a given time.

## **6. Validation**

A random sample of approximately 5 percent of the subjects will be drawn, and these subjects' data will be audited. Auditing will consist of comparing the data on the remote data capture screens, which are considered source data, to the following derived data sets:

1. the web report "patient event report"
2. the web report "follow-up time for survival analysis"
3. the statistician's working mortality data sets
4. the statistician's working secondary intervention data sets

Auditing will be done by people uninvolved in producing the derived data sets.

## 7. Web reports

### 7.1. General

All reports are available in Excel or PDF format and can be limited in any of the following ways:

1. whether to exclude compassionate use cases (default: do not exclude)
  - a. exclude (CLNO:COMPYN = "NO")
  - b. do not exclude (all cases)
2. type of device (default: all subjects):
  - a. fenestrated (PRTH:FORMTP1 = 1)
  - b. visceral (PRTH:FORMTP2 = 1)
  - c. hypogastric (PRTH:FORMTP3 = 1)
3. maximum subject number (default: all subjects)
4. maximum enrollment date (default: date on which the report is generated), which has the following effects:
  - a. a subject can be included only if his procedure date (PRTH:PROCDT) is less than or equal to the maximum
  - b. a follow-up form can be used only if the visit date (FIMG:APPTDT or FUP:EV\_DT) is less than or equal to the maximum
  - c. a subject can be counted as dead only if his death date (DTH:DTHDAT) is less than or equal to the maximum
  - d. a secondary intervention can be counted only if the procedure date (PRTH:PROCDT) is less than or equal to the maximum
  - e. the maximum is considered the last day of the reporting period in the definitions of follow-up time in sections 4 and 5

Events are reported at the following visits:

- pre-discharge (FIMG/FUP:CPEVENT = "PRE\_DISCHARGE")
- 1 month (FIMG/FUP:CPEVENT = "1 MONTH FUP")
- 6 months (FIMG/FUP:CPEVENT = "6 MONTH FUP")
- 12 months (FIMG/FUP:CPEVENT = "12 MONTH FUP")
- 24 months (FIMG/FUP:CPEVENT = "24 MONTH FUP")
- 36 months (FIMG/FUP:CPEVENT = "3 YEAR FUP")
- 48 months (FIMG/FUP:CPEVENT = "4 YEAR FUP")
- other (FIMG/FUP:CPEVENT = "OTHER")

## 7.2. Events: Summary report

All events will be included in a single report, which will have one column for each visit and two rows for each event, as follows:

event		pre-discharge	visit 1-month	(etc.)
endoleak, any	number yes	#	#	
	number yes or no	#	#	
endoleak, type I	number yes	#	#	
	number yes or no	#	#	
(etc.)				

### 7.3. Events: Patient-level data set

Each event will have its own report, with one column for each visit and one row for each subject, as follows:

event = endoleak, any

patient	visit		
	pre-discharge	1-month	(etc.)
1	0/1/missing	0/1/ missing	
2	0/1/ missing	0/1/ missing	
(etc.)			

event = endoleak, type I

patient	visit		
	pre-discharge	1-month	(etc.)
1	0/1/ missing	0/1/ missing	
2	0/1/ missing	0/1/ missing	
(etc.)			

(etc.)

#### 7.4. Mortality and secondary interventions

The summary reports will consist of the tables described in sections 4 and 5. The patient-level reports will have one row for each subject and the following columns:

Mortality:

1. study ID (CLNO:PT)
2. Cleveland Clinic ID (CLNO:CLINNO)
3. procedure date (PRTH:PROCDT)
4. discharge date (PRTH:DSCHDAT)
5. date of end of follow-up period, as defined in section 4.1
6. length of follow-up period in months, as defined in section 4.1
7. indicator of whether subject is dead (0 = no, 1 = yes)
8. indicator of whether death is AAA-related, as defined in section 4.3 (0 = no, 1 = yes, NULL = not dead)

Secondary interventions:

1. study ID (CLNO:PT)
2. Cleveland Clinic ID (CLNO:CLINNO)
3. procedure date (PRTH:PROCDT)
4. discharge date (PRTH:DSCHDAT)
5. date of end of follow-up period, as defined in section 5
6. length of follow-up period in months, as defined in section 5
7. indicator of whether subject has had at least one secondary intervention (0 = no, 1 = yes)
